Official Title: The effects of spasticity on glucose metabolism and soft tissue body composition in individuals with motor complete and motor incomplete spinal cord injury

NCT03859960

Document date: August 6th, 2020

Study Protocol:

Objective: Investigators aimed to assess the effects of spasticity on glucose metabolism and body composition in individuals with motor complete and incomplete SCI.

Methods: This prospective, cross-sectional study was conducted at the inpatient rehabilitation unit of a training and research hospital from September 2014 to May 2018. Participants with SCI were included to study if times from injury were at least one year. Participants had an AIS grades of A-D with spasticity. Spasticity was assessed with Penn Spasm Frequency Scale (PSFS) and Modified Ashworth Scale (MAS). Hip adductor and extensor spasticity, knee extensor and flexor spasticity and ankle plantar flexor spasticity were assessed by using MAS. Body composition was measured by dual-energy x-ray absorptiometry. All participants underwent a 75 gram (g) oral glucose tolerance test (OGTT). Insulin sensitivity and insulin resistance were assessed by calculating Matsuda index and HOMA-IR. Investigators assessed the effects of spasticity on glucose metabolism and body composition in participants with SCI.

Statistical analysis

The IBM SPSS Statistics 22 (IBM SPSS, Turkey) program was used for the statistical analysis. Normal distribution was evaluated using the Shapiro-Wilk test. Descriptive statistics of mean, SD, and frequencies were calculated. Pearson correlation analysis was used to assess the association between the parameters with conformity to the normal distribution. Statistical significance was evaluated at $p < 0.05$.

Results: With regard to the ASIA impairment scale 14 patients were classified as grade A and B (motor complete injured) and the remaining 19 were classified as grade C and D (motor incomplete injured). There was a positive correlation between hip adductor spasticity and trunk, android and gynoid percent fat-free masses (FFM%), and between hip extensor spasticity and android FFM% in

patients with motor complete SCI. There was a negative correlation between hip extensor and knee flexor spasticity and HOMA index; and positive correlation between hip adductor and extensor, knee flexor and extensor spasticity and Matsuda index in these patients. There was a positive correlation between knee extensor spasticity and gynoid FFM% and also, between PSFS and arms, trunk, gynoid, and total FFM% in patients with motor incomplete SCI. There was a negative correlation between hip adductor and extensor spasticity, PSFS and level of fasting glucose in patients with motor incomplete SCI.

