Official Title: The effects of spasticity on glucose metabolism and soft tissue body composition in individuals with motor complete and motor incomplete spinal cord injury

NCT03859960

Document date: August 6th, 2020

Statistical analysis

The IBM SPSS Statistics 22 (IBM SPSS, Turkey) program was used for the statistical analysis. Normal distribution was evaluated using the Shapiro-Wilk test. Descriptive statistics of mean, SD, and frequencies were calculated. Pearson correlation analysis was used to assess the association between the parameters with conformity to the normal distribution. Statistical significance was evaluated at $p < 0.05$.

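### Do body composition results given only as percent fat-free mass leave the study's aim unanswered?

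*Protocol*

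**What the plan says.** The Protocol's Objective is broad: "Investigators aimed to assess the effects of spasticity on glucose metabolism and body composition in individuals with motor complete and incomplete SCI". The title narrows body composition to soft tissue. The Methods give the instrument, "Body composition was measured by dual-energy x-ray absorptiometry", without listing the variables taken from the scans.

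The Results give these body composition findings, all with FFM%:

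- Motor complete (n=14): "There was a positive correlation between hip adductor spasticity and trunk, android and gynoid percent fat-free masses (FFM" (cut just before the percent sign), "and between hip extensor spasticity and android FFM% in" the same group.
- Motor incomplete (n=19): "There was a positive correlation between knee extensor spasticity and gynoid FFM" percent, and also "between PSFS and arms, trunk, gynoid, and total FFM% in patients with motor incomplete SCI".

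The abbreviation is spelled out once, but its denominator is not given. The SAP names no body composition variable. Its only statement on association is "Pearson correlation analysis was used to assess the association between the parameters with conformity to the normal distribution".

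**The concern.** A percentage has two moving parts. If FFM% is fat-free mass divided by fat-free plus fat mass, it rises when fat-free mass rises, when fat falls, or when both fall but fat falls further. A reader who sees nine positive correlations may conclude that spasticity goes with preserved muscle, when less fat would give the same sign. Body composition is one of the two stated targets, and scans that could supply the components already exist. An undefined denominator adds doubt about whether bone or whole-body weight enters the ratio. At stake is the meaning of every body composition result in the document.

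**Working it through.** **Count.** Motor complete: 3 + 1 = 4. Motor incomplete: 1 + 4 = 5. Total 9, all FFM%. The documents give no coefficient, mass or SD, so there is no figure of theirs to reproduce. Every mass, SD and correlation below is an assumption.

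**Same percentage by different routes.** Start from 10 kg fat-free and 5 kg fat: 10/15 = 66.7%. Then 12.5/17.5, 10/14 and 11.18/15.65 all equal 71.4%. They represent lean gain only, fat loss only, and both. Adding an assumed 0.6 kg of bone to the denominator gives 64.1% at the start and 69.1%, 68.5% and 68.8% after. The direction is the same and the ambiguity remains, so including bone barely alters the reading.

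**Correlation with the ratio.** Let F be fat-free mass, M fat mass and S spasticity, with FFM% = F/(F+M). To first order,

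r(S, FFM%) ≈ (a·r_F − b·r_M) / √(a² + b² − 2ab·r_FM), where a = mean M × SD F and b = mean F × SD M.

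Assume F has mean 25 kg and SD 3, and M has mean 12 kg and SD 2, 3 or 4. Then a = 36 and b = 50, 75 or 100. With F and M independent given S, r_FM = r_F·r_M. Worked at fat SD 2:

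- Fat only (r_M = −0.6): 30/√(1296 + 2500) = 30/61.6 = 0.49.
- Lean only (r_F = +0.6): 21.6/61.6 = 0.35.
- Mainly lean loss (r_F = −0.6, r_M = −0.3): (−21.6 + 15)/√(3796 − 648) = −6.6/56.1 = −0.12.

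Simulation agrees with the first-order formula within about 0.02:

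| Assumed link with S | fat SD 2 | fat SD 3 | fat SD 4 |
|---|---|---|---|
| fat −0.6, fat-free 0 | 0.48 | 0.54 | 0.56 |
| fat-free +0.6, fat 0 | 0.35 | 0.25 | 0.19 |
| fat −0.7, fat-free −0.2 | 0.48 | 0.58 | 0.61 |
| fat-free −0.6, fat −0.3 | −0.12 | 0.02 | 0.10 |

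With fat-free SD 5 and fat SD 2 the order of the first two rows reverses (0.37 and 0.46). With equal coefficients of variation (15% or 25%) they coincide, at 0.42 each. So neither sign nor size identifies the tissue. The last row shows that the sign still carries information: a clearly positive correlation is hard to reconcile with a predominant loss of fat-free mass. If both masses rise with spasticity at about 0.6 and have equal coefficients of variation, the correlation with FFM% is about 0, so the ratio removes a plain body-size effect.

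**What adding the components would yield.** Suppose six spasticity scores (five Ashworth muscle groups plus PSFS), six regions (the five named plus legs) and two groups are fully crossed: 6 × 6 × 2 = 72. With three outcomes this becomes 216, or 144 more. If all were null, 72 × 0.05 = 3.6 would fall below 0.05, against 216 × 0.05 = 10.8.

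Fisher intervals are tanh(atanh r ± 1.96/√(n−3)). For r = 0.5:

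- n=14: 0.549 ± 0.591, giving −0.04 to 0.81.
- n=19: 0.549 ± 0.490, giving 0.06 to 0.78.

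For r = 0 the limits are ±0.53 and ±0.45. A true fat-only pattern and a true lean-only pattern could easily give overlapping intervals for both components.

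**The case for a change.** The strongest case for a change is that the remedy is cheap. One sentence would define the denominator. The components come from scans already taken, FFM% could stay the main measure, and estimates with intervals need not be read as tests. Whether spasticity goes with more lean tissue or less fat is a natural question under an aim that names body composition, and the reported results do not answer it.

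Much of this stands. The denominator is missing, and the results speak to relative composition only. What does not stand is the step from there to a defect:

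- Each result is worded as a percentage and no claim is made about a particular tissue, so there is no statement to correct.
- Composition is readily understood as relative. Separating the tissues in kilograms is a further question that the documents do not set themselves.
- The Results are a short summary naming only correlations that were found. Absolute masses may have been analysed and found unremarkable, so their absence from the summary does not show that they were ignored.
- Raw kilograms vary with body size and sex, which FFM% partly scales out. Adding unadjusted correlations in kilograms would bring that confounding back, and adjusting for it is costly with 14 and 19 patients.

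**Conclusion.** No change to the plan is needed. The observation is accurate: nine of nine reported body composition correlations use a ratio whose denominator is unstated, and the ratio alone does not tell fat-free gain from fat loss. The reported findings nonetheless remain sound as statements about relative composition, and their positive sign makes a predominant loss of fat-free mass unlikely. The missing denominator is a detail that an analyst would fill in when writing up. Absolute masses would be a debatable addition: up to 144 further, mathematically linked correlations on the assumed grid, with intervals as wide as −0.04 to 0.81 at n=14, and no assurance that the tissues would separate.

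This rests on the denominator being fat-free plus fat mass, with or without bone, and on illustrative masses and SDs that are not in the documents. The qualitative conclusion depends little on those values. It would change only if the study claimed an effect on fat-free mass itself, which neither document does.

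### Neurological level is neither reported nor adjusted for, so if tetraplegia and paraplegia were both enrolled, the arms, trunk and total FFM% correlations may be confounded or diluted

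*Protocol*

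**What the plan says.** Under Methods, the protocol gives the entry conditions as "Participants with SCI were included to study if times from injury were at least one year" and "Participants had an AIS grades of A-D with spasticity". Neither sentence limits neurological level, and the word does not appear in either document as a criterion, descriptive variable, stratum or covariate.

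The only division of the sample is by completeness. The Results put it as "14 patients were classified as grade A and B (motor complete injured"); the other group, called motor incomplete, holds 19 participants with AIS C or D.

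The SAP, under Statistical analysis, names one method of association: "Pearson correlation analysis was used to assess the association between the parameters with conformity to the normal distribution". It mentions no covariate and no partial correlation. The protocol's statistical section carries the same text.

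On the exposure side, "Hip adductor and extensor spasticity, knee extensor and flexor spasticity and ankle plantar flexor spasticity were assessed by using MAS", so every muscle group graded by MAS is in the lower limb. PSFS is the other spasticity measure.

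On the outcome side, the Results list positive associations in the motor incomplete group "between PSFS and arms, trunk, gynoid, and total FFM% in patients with motor incomplete SCI". In the motor complete group, trunk FFM% is among the outcomes associated with hip adductor MAS. No coefficients or p-values are given.

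**The concern.** AIS grade describes how complete a lesion is, not where it is. Splitting by AIS therefore does nothing to separate tetraplegia from paraplegia. For arms FFM%, and to a large extent trunk FFM%, level decides whether the measured tissue is above or below the lesion, and total FFM% inherits part of that difference. In paraplegia the arms are above the lesion, so a direct action of spasticity on arm tissue is hard to argue. Yet the stated objective is to assess effects of spasticity on body composition, and arms FFM% is among the results.

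If both levels are present, two things can go wrong with a crude correlation. Where level is related to both the spasticity score and FFM%, some of the coefficient reflects a difference between levels. Where level shifts FFM% but not the score, the extra spread pulls the coefficient towards zero. At stake are three of the eight motor incomplete results (PSFS with arms, trunk and total FFM%) and the trunk result in the motor complete group.

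**Working it through.** **Count of results.** Motor incomplete group: knee extensor MAS with gynoid FFM% (1); PSFS with arms, trunk, gynoid and total FFM% (4); hip adductor MAS, hip extensor MAS and PSFS with fasting glucose (3). 1 + 4 + 3 = 8. Arms, trunk and total are the three to which the level argument applies.

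**Inputs from the documents.** n=14 and n=19 (sum 33); significance level 0.05. Two-sided testing is assumed because sidedness is not stated. There is no sample-size figure, coefficient or level distribution to reproduce.

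**Assumed inputs.** p = share with tetraplegia; D and E = shift of FFM% and of the spasticity score in tetraplegia, in within-level SD units; r = within-level correlation, taken as equal in both levels. Both variables are treated as normal within level, which is a simplification for ordinal scores such as PSFS and MAS.

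**Pooled correlation.**

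pooled r = [r + p(1−p)DE] / √{[1 + p(1−p)D²][1 + p(1−p)E²]}

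*Confounding: r = 0, p = 0.5, D = E.*
- 0.5 SD: 0.0625 / 1.0625 = 0.06
- 1.0 SD: 0.25 / 1.25 = 0.20
- 1.5 SD: 0.5625 / 1.5625 = 0.36

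Simulated rejection rates at n=19 with about half tetraplegia:

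| Shift in both variables | Crude | With level term |
|---|---|---|
| 0.5 SD | about 5.5% | 5% |
| 1.0 SD | 13% | 5% |
| 1.5 SD | 36% | 5% |

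At n=14 with 1.0 SD shifts the crude rate is about 11%.

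*Dilution: r = 0.5, p = 0.4, E = 0.*
- D = −1.0: 0.5 / √1.24 = 0.45
- D = −1.5: 0.5 / √1.54 = 0.40

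At n=19, crude power is 50% and 40% respectively, against 59% with a level term.

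*Settings with no spurious association.* If only one level is present (p = 0 or 1), the formula returns r unchanged. If r = 0 and the score is unrelated to level (E = 0), the pooled r is 0 and rejection stays at about 5%.

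*Opposite-direction shifts: r = 0, n=19, about 40% tetraplegia.* If FFM% is 1.0 SD lower and the score 0.5 to 1.0 SD higher in tetraplegia, a significant positive correlation arises in only 0.8% to 0.2% of data sets, below the nominal 2.5% for that tail.

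**Cost of the level term.** Critical |r| = t/√(df + t²), with df = n−2 crude and n−3 adjusted.
- n=19: t = 2.110 on 17 df gives 0.456; t = 2.120 on 16 df gives 0.468.
- n=14: t = 2.179 on 12 df gives 0.532; t = 2.201 on 11 df gives 0.553.

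**Paraplegia subset.** With 40% tetraplegia, 0.6 × 19 is about 11 participants. Critical |r| is 0.60, and power at a true r of 0.5 is just over 36%.

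**The case against.** The strongest reply is that the documents do not show a mixture of levels. A reader might infer that the outcomes were pooled over all neurological levels, and that each coefficient is therefore biased or diluted. The documents support neither step. They are silent on level, so enrolment of tetraplegia is possible but not established, and several plausible mixtures leave the correlation nearly or wholly undistorted.

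A second stronger reading is that the positive PSFS results are artefacts of level. That requires FFM% and the score to shift in the same direction. If FFM% is lower in tetraplegia, PSFS would have to be lower there too, and nothing in the documents says so. With opposite shifts, spurious positive results become rarer. Nor does lost power through dilution cast doubt on associations already reported as significant; it bears on associations that may have been missed.

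Two limits of scope also stand. It would be tempting to contrast paralysed with normally innervated tissue, but the arms and total results come from AIS C and D participants, who keep some motor function below the lesion, so the contrast is less sharp. Gynoid FFM% is a hip-region measure, to which the arms and trunk argument does not extend.

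What the reply does not remove is the gap itself: level bears on what arms, trunk and total FFM% represent, and the reader cannot tell whether it matters here.

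**Conclusion.** The point holds as an unaddressed possible confounder or source of dilution, not as a demonstrated bias. It applies to PSFS with arms, trunk and total FFM% in the motor incomplete group, and to trunk FFM% in the motor complete group. It is conditional on both levels having been enrolled.

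The size is unknown. Under the assumed same-direction shifts, the excess false-positive risk is negligible at 0.5 SD, moderate at 1.0 SD and large only at 1.5 SD in both variables at once. These figures rest wholly on assumed level inputs and show what could happen, not what did. The case for acting is that the remedy is cheap and that one reported table row could close the question.

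**What to change.** Report the number of participants with tetraplegia and with paraplegia in each AIS group. If only one level is present, say so; nothing further is needed.

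If levels are mixed, give partial correlations adjusted for a binary level term for the FFM% outcomes, with 95% confidence intervals, beside the crude values. Show the association of PSFS with arms FFM% descriptively within paraplegia, stating that the subset is too small for a firm test. If the arms, trunk or total estimates shrink materially on adjustment, qualify the statement that they reflect an effect of spasticity. Do not withdraw a result merely because its p-value crosses 0.05: at these sample sizes that can happen without any confounding.

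The cost is one degree of freedom per test and a re-run of the correlations. Level should be available from the neurological examination that gave the AIS grade, although the documents do not confirm that it was recorded. The binary term has limits that should be stated: it assumes the same slope in both levels, so it does not address a spasticity association that differs by level, and it captures trunk innervation only coarsely because paraplegia covers both high and low thoracic lesions.

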Official Title: The effects of spasticity on glucose metabolism and soft tissue body composition in individuals with motor complete and motor incomplete spinal cord injury

NCT03859960

Document date: August 6th, 2020

Statistical analysis

The IBM SPSS Statistics 22 (IBM SPSS, Turkey) program was used for the statistical analysis. Normal distribution was evaluated using the Shapiro-Wilk test. Descriptive statistics of mean, SD, and frequencies were calculated. Pearson correlation analysis was used to assess the association between the parameters with conformity to the normal distribution. Statistical significance was evaluated at $p < 0.05$.

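### The FFM% correlations have no sex term: if both sexes were enrolled and FFM% differs by sex, they may be diluted or biased in either direction

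*SAP*

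**What the plan says.** The SAP's Statistical analysis section, repeated in the protocol, gives a single association method: "Pearson correlation analysis was used to assess the association between the parameters with conformity to the normal distribution". Significance is set at p < 0.05, with sidedness not stated. No partial correlation, regression, covariate or sex stratum appears.

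On eligibility, the protocol's Methods say "Participants with SCI were included to study if times from injury were at least one year", and add AIS grade A to D and the presence of spasticity. Sex is mentioned nowhere: there is no criterion, no count and no sex-specific FFM%. The design is described thus: "This prospective, cross-sectional study was conducted at the inpatient rehabilitation unit".

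The only split is by motor completeness. The Results give "14 patients were classified as grade A and B (motor complete injured" and "remaining 19 were classified as grade C and D (motor incomplete injured". Nine body-composition associations are reported, all positive and all on FFM%:

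- Four in the motor complete group: hip adductor spasticity with the trunk, android and gynoid regions ("There was a positive correlation between hip adductor spasticity and trunk, android and gynoid percent fat-free masses (FFM"), and hip extensor spasticity with the android region.
- Five in the motor incomplete group: knee extensor spasticity with the gynoid region, and four with the Penn scale ("between PSFS and arms, trunk, gynoid, and total FFM% in patients with motor incomplete SCI").

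No coefficients or p-values are given.

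**The concern.** A simple correlation leaves everything else that affects FFM% in the comparison. If men and women differ in FFM%, sex can act in two ways. Where it is unrelated to spasticity, it adds outcome variance that spasticity cannot explain, so the coefficient shrinks on average and a real association is easier to miss. Where it is related to spasticity, it confounds the coefficient, which can then be too large, too small or of the wrong sign.

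Body composition is half of the study's objective, and one omission would touch all nine reported FFM% results as well as the FFM% pairs not reported. With 14 and 19 patients there is little room for either problem. Without the sex mix, a reader cannot judge whether either one applies.

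**Working it through.** The documents give no sample size calculation, power or target correlation, so there is no figure of theirs to reproduce.

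**Inputs from the documents:** n = 14 and n = 19; significance level 0.05 (taken as two-sided); no covariate.

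**Assumed inputs:** share of women q, here 4/14 and 5/19; sex gap in FFM% of d = 1.5 within-sex SD, varied from 0.5 to 2.0; correlation given sex ρ = 0.6, with 0.5 as an alternative; sex–spasticity correlation a; sex–FFM% correlation b. Scores are treated as continuous and normal, so the results are approximate for ordinal spasticity grades.

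**1. Significance threshold.** Critical |r| = t/√(t² + df), with df = n−2 unadjusted and n−3 with sex removed.

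- n=14: 2.179/√(4.748+12) = 0.532; adjusted 2.201/√(4.844+11) = 0.553.
- n=19: 2.110/√(4.452+17) = 0.456; adjusted 2.120/√(4.494+16) = 0.468.

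**2. Dilution when sex is unrelated to spasticity (a = 0).** The sex share of FFM% variance is b² = q(1−q)d²/(1+q(1−q)d²), and the pooled correlation is ρ√(1−b²).

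- n=14: q(1−q)d² = 0.204 × 2.25 = 0.459; b² = 0.459/1.459 = 0.315; pooled r = 0.6 × √0.685 = 0.50.
- n=19: 0.194 × 2.25 = 0.436; b² = 0.436/1.436 = 0.304; pooled r = 0.6 × √0.696 = 0.50.

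**3. Power when a = 0.** Simulation with 40,000 samples per case and ρ = 0.6 compared the pooled correlation with the correlation after centring both variables within sex:

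| Case | n=14, pooled / adjusted | n=19, pooled / adjusted |
|---|---|---|
| Gap 1.5 SD; 4 of 14, 5 of 19 women | 45% / 63% | 61% / 79% |
| Gap 1.0–2.0 SD; 2–6 of 14, 3–8 of 19 women | 31–59% / 62–63% | 44–75% / 79% |
| Gap 0.5 SD; 4 of 14, 5 of 19 women | 63% / 63% | 79% / 79% |

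In the 1.5 SD case, the pooled |r| was larger than the adjusted one in 22% of samples at n=14 and 18% at n=19. With no true association, both methods rejected in about 5% of samples.

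Fisher-z power with ρ = 0.5 and q = 0.3 gives the same pattern. At a 1.5 SD gap it is 30% against 41% (n=14) and 42% against 56% (n=19). At 0.5 SD it is 42% against 41%, and about 56% for both. A degree of freedom spent for nothing, as in a one-sex sample, takes power from 44% to 41% and from 59% to 56%.

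**4. Bias when sex is related to spasticity.** Pooled r = ab + ρ√((1−a²)(1−b²)).

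- ρ = 0.5, a = 0.4, b = 0.5: 0.20 + 0.5 × √(0.84 × 0.75) = 0.20 + 0.40 = 0.60.
- Same with a = −0.4: −0.20 + 0.40 = 0.20.
- ρ = 0.3, a = −0.4, b = 0.7: −0.28 + 0.3 × √(0.84 × 0.51) = −0.08, a reversed sign.
- ρ = 0, a = 0.4, b = 0.5: pooled r = 0.20, and a nominal 5% test rejects in 10% (n=14) or 13% (n=19) of samples.

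**5. Chance imbalance.** Even if sex and spasticity are independent, a has SD 1/√(n−1), which is 1/√13 = 0.28 and 1/√18 = 0.24. So |a| exceeds 0.2 in about 50% and 42% of samples.

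**The case against.** The strongest objection is that the premise is not documented. An eligibility rule that is silent on sex does not show that both sexes were enrolled, and no sex gap in FFM% is given. This stands, and it makes the point conditional. In a one-sex sample there is nothing to adjust for.

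A reader might infer that leaving sex out dilutes every FFM% coefficient and costs power throughout. The documents do not support that. Dilution is an average effect that assumes sex is unrelated to spasticity. Under that very assumption, about one sample in five has the larger coefficient before adjustment. Spasticity is also observed here, not assigned, so independence cannot be taken for granted.

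It is also fair to say that lost power is the wrong worry for the nine reported results, since all nine are presented as positive findings. For them, inflated or spurious association matters at least as much. Lost power bears on the FFM% pairs that were not reported.

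Finally, results are already written, so making an adjusted coefficient the main result now would be a post hoc change of analysis. That objection also stands and shapes the fix. None of these objections removes the gap: the plan neither reports the sex mix nor gives an adjusted estimate.

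**Conclusion.** The concern holds conditionally. It rests on two assumptions that the documents neither confirm nor contradict: that both sexes were enrolled, and that FFM% differs by sex.

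- If sex is unrelated to spasticity, the unadjusted analysis gives up about 18 points of power at either group size in the middle case (63 − 45 and 79 − 61). It gives up nothing at a 0.5 SD gap, and adjusting a one-sex sample would itself lose about 2 to 3 points.
- If sex is related to spasticity, the direction of bias is unknown and the false-positive rate can pass 5%; 10% and 13% in the example above.

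It would go too far to conclude that the nine reported associations are wrong, or that they are understated. No coefficients, sex counts or sex-specific FFM% are given, so either error is possible and neither is shown. The point is worth acting on because the check is cheap and its result decides how far the FFM% findings can be relied on.

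**What to change.** In the Statistical analysis section:

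1. Report the number of men and women in each motor group.
2. Where both sexes are present, add for every FFM% outcome a partial correlation adjusted for sex, or a linear model with spasticity score and sex. Show it beside the planned unadjusted coefficient, and label it as added after the data were seen. The planned coefficient is not replaced.
3. State which FFM% associations hold after adjustment and limit the conclusions to those.

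The cost is a few sentences and a re-run on existing data, provided sex was recorded. Statistically it takes one degree of freedom per correlation, which raises the critical |r| from 0.532 to 0.553 at n=14 and from 0.456 to 0.468 at n=19. If a group turns out to be of one sex, the count alone settles the matter there and no adjustment is needed.
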